## **9.6 DATA MANAGEMENT**

All established security and confidentiality procedures will be observed by BI and/or personnel who are assigned appropriate access to the data. Enrolment data, medical claims, and prescription claims will be accessed from this administrative claims dataset. The analyses will be performed on limited data sets that are void of member protected health information and all results were shared in aggregate form only.

## **9.7 DATA ANALYSIS**

### **9.7.1 Main analysis**

We will provide the sample attrition at each step of the inclusion-exclusion criteria as well as a baseline demographic and comorbidity breakdown. We will provide a comparative breakdown in baseline measures for the unmatched and matched cohorts to assess if PSM eliminated baseline differences. For the primary endpoints analysis, we will calculate the time to first exacerbation per patient and compare it between the two groups (Tio vs. NonTio). For secondary endpoint analyses we will compare the rate of exacerbation, proportion of patients with exacerbations after 6 months and one year (based on Kaplan Meier estimates), HCRU and average cost during follow-up and compare them between the two groups (Tio vs. NonTio).

The primary outcome of the study will be analyzed using Cox proportional hazard modelling. The secondary outcome of rate of exacerbation per patient will be analyzed using negative binomial regression. This technique works on the assumption that the rate of exacerbation varies among every subject in the study ([P16-06846](#)). Also this model accounts for overdispersion of data which is likely to happen due to variability between the patients. Balance in covariates will be checked after matching. If PSM was able to balance all observed baseline characteristics, the regression models for outcomes will be limited to the databases (IMS and EMR) and to the key independent variable of interest (namely Tio use vs. ICS/LABA dose increase) and model overfitting is not, therefore, of concern. However, if there are unbalanced baseline characteristics, we will include these characteristics in the regression as covariates. For regression model covariate selection we

will also estimate the multicollinearity of covariates by assessing their correlations of independent variables. For example, if comorbidities from the specific list are also included in CCI, they will only be included in the CCI.

In order to handle missing data, in the PSM we will create a category variable (‘missing data’) for each covariate to ensure that patients with that variable and without that variable are respectively matched. Patients with missing prescription data required for classification of the treatment groups will be excluded. Patients with missing lung function scores and ACT scores at baseline and in the follow up period will be excluded from these respective secondary analyses.

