## 9.11 SUBJECTS

1. Patients with least one asthma diagnosis in the inpatient setting or at least two separate instances of asthma diagnosis (separated by at least 30 days) recorded in the outpatient or emergency room setting will be included (ICD 9 CM: 493.xx or ICD 10: J45-J45.999).
2. Patients will be required to be already on ICS/LABA.
3. Patients below the age of 6 years on the ICS/LABAI date will be excluded.
4. Patients will be required to have available records 12 months prior to the index date (6 months will be used if patient exclusions due to this criteria adversely affect the study sample size).
5. Patients with a diagnosis of COPD at any time during the study period will be excluded.
6. Those who are on biologics at baseline will be removed.
7. After the PSM process, unmatched patients will be excluded.

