## 9.12 BIAS

### Channeling Bias Mitigation

Introduction of channeling bias in this study is highly likely using retrospective claims data based on asthma medication use; patients between the two cohorts may differ in baseline control and severity levels. On aggregate, patients for whom Tiotropium Respimat® 1.25 mcg was added (vs NonTio) are likely to be less well-controlled and more severe both at baseline and during the follow up period. Absent a method to control for this channeling bias, it is likely that placing sicker patients in the Tiotropium Respimat® 1.25mcg group will confound an accurate comparison of cost, resource use, and other outcomes between the groups. Two design features of our study will help mitigate this bias. First, our comparison (NonTio) group will be required to step-up their baseline ICS/LABA dose or have an additional prescription/refill of high-dose-ICS/LABA following the first prescription of baseline high dose ICS/LABA within the study period. Second, we will use Propensity Score Matching (PSM) to match patients on key measures of disease control and severity as listed in [Table 1](#), such as demographics, Charlson Comorbidity Index (CCI) score, specific comorbidities, number of prescriptions (overall and asthma-related medications). This baseline matching strategy will be particularly important to ensure that patients in the TIO group who have a corresponding increase in their ICS dose at or prior to the date of their TIO prescription (for example, if the patient has an exacerbation), will be matched to a corresponding NonTIO patient in terms of increased ICS dose or additional ICS prescription. It should be noted that after the prescription index date for both Tio and NonTio patients, we anticipate changes in ICS medication for patients in both cohorts. These ICS medication changes reflect patient

outcomes in the follow-up period, where patients who encounter exacerbation in either group are likely to see a change in the ICS dose.

As a result, post-index period ICS medication changes will not alter the classification of patient groups nor will it be the basis for exclusion of these patients.

We will conduct 1:2 matching using a nearest neighbour matching approach with a radius of  $0.2 * SD(\log(P))$ . This will be conducted in both databases (IMS: Cohort I and EMRClaims+: Cohort II) separately.

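### If matching leaves a prognostic imbalance, section 9.7.1 adjusts the Cox hazard ratio but not the 6-month and one-year Kaplan-Meier proportions

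*Combined protocol and SAP*

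**What the plan says.** All of the analysis wording is in section 9.7.1 of the combined protocol and SAP.

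- **Primary outcome:** "The primary outcome of the study will be analyzed using Cox proportional hazard modelling".
- **Exacerbation rate:** "The secondary outcome of rate of exacerbation per patient will be analyzed using negative binomial regression".
- **Absolute risks:** the groups are also compared on the "proportion of patients with exacerbations after 6 months and one year (based on Kaplan Meier estimates"). No weighting, stratification, standardisation, test or confidence interval is named for these.
- **Balance:** "Balance in covariates will be checked after matching". No numerical threshold is given. If balance is reached, "the regression models for outcomes will be limited to the databases (IMS and EMR) and to the key independent variable of interest". If it is not, "if there are unbalanced baseline characteristics, we will include these characteristics in the regression as covariates".

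The cohort is defined elsewhere. Section 9.11 states: "After the PSM process, unmatched patients will be excluded". Section 9.12 specifies the matching ("We will conduct 1:2 matching using a nearest neighbour matching approach with a radius of" 0.2 SD), done separately in each database. The same section calls channeling bias highly likely and expects Tio patients to be the less well controlled and more severe group.

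**The concern.** The plan foresees that matching may leave some characteristics unbalanced, and it judges this serious enough to adjust for. The adjustment it describes reaches only outcomes that have a regression model. The 6-month and one-year proportions come from the same event times as the primary Cox analysis but have no model, so in that case they would be reported without the correction.

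These proportions are the only cumulative exacerbation risks the plan names. Section 7 gives the intended audience as health systems, payers and prescribers, who are likely to read absolute risks directly. If the imbalance runs in the direction section 9.12 expects, the raw proportions would show a smaller Tio benefit than the adjusted hazard ratio implies. The choice between raw and adjusted proportions would then be made after results are seen.

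**Working it through.** **Step 1, the text.** Section 9.7.1 ties a model to two outcomes: Cox to time to first exacerbation and negative binomial to the rate. The imbalance remedy acts through added covariates. A Kaplan-Meier estimate has none, so the remedy cannot reach the proportions. The abstract adds only that time to first exacerbation is compared descriptively and by Cox. The proportions do use the matched cohort, because unmatched patients are excluded. The gap is therefore limited to imbalance that remains after matching.

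**Step 2, inputs from section 9.5.** 6.4% with an event by 5.5 months gives −ln(1 − 0.064)/5.5 = 0.01203 per month, which reproduces the stated 0.012. The Tio rate of 0.0096 gives a hazard ratio of 0.0096/0.012 = 0.80. The second scenario, 0.028 and 0.0224 per month, also gives 0.80.

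**Step 3, assumptions not in the documents.** There is one binary risk factor with hazard ratio 2. Its prevalence after matching is p1 in Tio and p0 in NonTio. Hazards are constant and there is no censoring.

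**Step 4, formulas.** The baseline hazard is set so that the NonTio average is 0.012: h0 = 0.012/(1 + p0). The risk by month t in an arm with treatment hazard ratio H and prevalence p is

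R(p, H) = 1 − [(1 − p)·exp(−h0·H·t) + p·exp(−2·h0·H·t)].

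- Raw contrast: R(p0, 1) vs R(p1, 0.80).
- Contrast standardised to the matched Tio patients: R(p1, 1) vs R(p1, 0.80).
- Share lost: 1 − raw difference/standardised difference.

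**Step 5, one case in full (t = 12, p1 = 40%, p0 = 35%).** h0 = 0.012/1.35 = 0.008889.
- Survival under NonTio: exp(−0.10667) = 0.8988 without the factor and exp(−0.21333) = 0.8079 with it.
- Survival under Tio: exp(−0.08533) = 0.9182 and exp(−0.17067) = 0.8431.
- Raw NonTio: 1 − (0.65 × 0.8988 + 0.35 × 0.8079) = 13.30%.
- NonTio at the Tio mix: 1 − (0.60 × 0.8988 + 0.40 × 0.8079) = 13.76%.
- Tio: 1 − (0.60 × 0.9182 + 0.40 × 0.8431) = 11.18%.
- The standardised difference is 2.57 points (from unrounded risks) and the raw one 2.12. Share lost: 1 − 2.12/2.57 = about 18%.

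**Step 6, one-year results at 0.012 per month (NonTio vs Tio).**

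| Prevalence Tio / NonTio | Standardised difference in the factor | Adjusted contrast | Raw contrast | Effect lost |
|---|---|---|---|---|
| 37% / 35% | 0.04 | 13.5% vs 11.0% (2.52 points) | 13.3% vs 11.0% (2.34) | about 7% |
| 40% / 35% | 0.10 | 13.8% vs 11.2% (2.57) | 13.3% vs 11.2% (2.12) | about 18% |
| 40% / 30% | 0.21 | 14.2% vs 11.6% (2.66) | 13.3% vs 11.6% (1.72) | about 35% |

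The same formulas at 6 months, and at 0.028 per month, give nearly the same shares (7%, 17% to 18%, 35% to 36%).

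**Step 7, is this just conditional versus marginal?** An adjusted Cox hazard ratio and a Kaplan-Meier contrast can differ even without confounding. Here that gap is negligible. The hazard ratio implied by the standardised risks, ln(1 − R_Tio)/ln(1 − R_NonTio), is 0.80 in these rows. The raw risks imply 0.83 at 40%/35% and 0.86 at 40%/30%.

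**Step 8, when does the sign reverse?** Among the combinations tried, only in the most extreme: prevalence 55% vs 30% (standardised difference 0.52) and a factor hazard ratio of 3. The raw one-year risks are then 13.1% NonTio and 13.8% Tio, a difference of 0.7 points against Tio.

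**The case against.** The strongest reply is that matching is the plan's main control of confounding, and it serves the Kaplan-Meier estimates as much as the Cox model. That stands. If every measured characteristic is balanced, the matched proportions need no further adjustment for them, and it would be wrong to say that they are confounded as planned.

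Matching within each database also stands as an answer on database. If the 1:2 ratio is achieved throughout, the database mix is the same in both arms. Only incomplete match sets would disturb this.

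The prevalences and the hazard ratio of 2 are assumed. An obvious candidate for the factor, asthma control status, is a matching parameter in Table 1, with further matching of poorly controlled patients on admissions, visits and OCS use. A 10-point residual difference there may be unlikely, which is why the 2-point case is shown. Against this, the plan provides for residual imbalance itself, sets no threshold, and expects strong channeling.

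A reader might infer that the report would show harm, or that the two analyses would contradict each other. The plan's rates do not support that. In all three illustrated cases Tio still has the lower risk, so the effect is attenuation.

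Finally, this is a contingency on a secondary endpoint. The Cox and negative binomial analyses are unaffected, and section 9.9 says that no effectiveness claims should rest on the study. This limits how much the point matters but does not close the gap.

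**Conclusion.** The point holds in conditional form. If the balance check fails on a prognostic characteristic, the plan leaves the 6-month and one-year proportions in the matched cohort unadjusted for it, while the Cox hazard ratio is adjusted. With the expected channeling the bias runs against Tio. Under the stated assumptions about 7% to 35% of the one-year difference is lost for residual differences of 2 to 10 percentage points in a factor with hazard ratio 2. These are illustrations. The documents give no residual imbalance and no prognostic strength. The point merits a change to the plan because the trigger is one the plan already defines and the remedy is cheap.

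**What to change.** Add to section 9.7.1 that, if any characteristic is judged unbalanced after matching:

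- the 6- and 12-month proportions will also be reported standardised to the matched Tio patients;
- the model will be a Cox model stratified by treatment group, which avoids assuming proportional hazards between arms, with the unbalanced characteristics and database as covariates;
- each matched Tio patient's risk will be predicted under both arms and averaged, with bootstrap confidence intervals;
- the between-group comparison will use these standardised proportions, and the raw matched Kaplan-Meier curves will be shown as descriptive.

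If balance is achieved, the matched Kaplan-Meier estimates stand as planned. It would help to fix the balance threshold in advance, since it decides which version applies.

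The cost is a few sentences of SAP text and a few lines of code. There is a small downside: the standardised proportions depend on the covariate model, and they correct for measured covariates only.

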**Table 1: Matching Parameters**

Variable Name and Type	Description	Applicable to Study Cohort: 1=IMS, 2=EMRClaims+
ICS/LABA dose on ICS/LABAI date	The dose level of the first prescription on the ICS/LABAI date (low, medium, or high)	1 and 2
Demographics (categorical and continuous variables)	Age (10-year increments) and Gender Male/Female), Region (if available, Northeast, Midwest, South, West)	1 and 2
CCI (continuous variable)	Charlson Comorbidity Index score	1 and 2
Specific comorbidities (categorical variables)	Cardiovascular conditions, cerebrovascular diseases, hypertension, diabetes, metabolic and endocrine comorbidities, anxiety and depression, gastro-esophageal reflux disease, cancer and obesity identified using appropriate ICD codes. All above measures will be coded as binary (yes/no) variables.	1 and 2
Medications (categorical variable)	Polypharmacy level matched within a range of 2 drugs (for example, 0-2,3-5,6-8,8-10 and so on).	1 and 2
Asthma Control Status: Well Control or Poor Control (categorical variable)	‘Well Controlled’ if patient has no prescriptions for an OCS, and no asthma-related emergency department visits or hospitalizations other than the first diagnosis recorded in the data extracted (Ref: Stempel JACI 2005). Categories will include Well Controlled and Not Well Controlled.	1 and 2
Hospital admissions Outpatient visits ER visits and OCS use (categorical variables)	Poorly Controlled patients (“Not Well Controlled”) will further be matched based on the presence of asthma-related admissions, outpatient visits, and ER visits or use of OCS during the pre-index period.	1 and 2
Eosinophil levels (EMRClaims+ database only) (categorical variables)	Eosinophil level categories: <150 cells/μL, 151-300cells/μL, 301-400 cells/μL, ≥400 cells/μL (as available)	2
Asthma Control Test (ACT) results (EMRClaims+ database only) (categorical variables)	ACT score categories developed based on data distribution (as available)	2

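### As written, the collinearity example in section 9.7.1 denies a comorbidity inside the CCI its own model term, even when it is left unbalanced after matching

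*Combined protocol and SAP*

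**What the plan says.** Section 9.7.1 sets out the adjustment strategy in three steps.

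- After matching there is a check: "Balance in covariates will be checked after matching". No balance metric or threshold is given. If everything is balanced, the outcome models contain only the database and the treatment group, so the CCI is not a standing covariate.
- If something is not balanced, the commitment is general: "if there are unbalanced baseline characteristics, we will include these characteristics in the regression as covariates".
- For covariate selection, the analysts "will also estimate the multicollinearity of covariates by assessing their correlations of independent variables". No correlation cut-off is stated. The illustration that follows reads "if comorbidities from the specific list are also included in CCI, they will only be included in the CCI".

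Table 1 lists the two kinds of variable as separate matching parameters. One is the continuous "Charlson Comorbidity Index score". The other is a set of binary indicators for "Cardiovascular conditions, cerebrovascular diseases, hypertension, diabetes, metabolic and endocrine comorbidities, anxiety and depression, gastro-esophageal reflux disease, cancer and obesity". Each can therefore be balanced or unbalanced on its own.

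No other section restores the dropped term or plans a sensitivity analysis that includes it.

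**The concern.** The second and third steps pull against each other. One says an unbalanced characteristic goes into the model. The other says that a comorbidity inside the CCI is represented only by the score, with no exception for one found unbalanced.

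A summed score is a poor stand-in for one of its parts. Two groups can have the same mean CCI while one has more of a given condition and the other has more of something else. The score gives every point the same slope, whatever condition it came from.

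At stake is confounding that the plan has already detected and intended to remove. It could remain in the hazard ratio for time to first exacerbation, in the exacerbation rate ratio, and in any adjusted comparison of resource use or cost. Section 9.12 expects the Tio group to be the sicker one. If the residual imbalance follows that pattern, and the comorbidity raises risk, the bias would run against Tio. The opposite imbalance would favour it.

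**Working it through.** The plan gives no figure for this rule, so the main check is textual and the arithmetic is illustrative.

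**What the text implies for an unbalanced CCI component**

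- (a) CCI total balanced: the CCI has no reason to enter, and the comorbidity has no term of its own. The model is database plus treatment, and the detected imbalance is wholly unadjusted.
- (b) CCI total also unbalanced: the CCI enters with one slope. Adjustment is complete only if the comorbidity's effect per CCI point equals that of the other points.

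**Inputs**

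- From section 9.5: 2,100 Tio and 4,200 NonTio; hazards of 0.028 versus 0.0224 per month over 11 months (PRIMO-based), and 0.012 versus 0.0096 per month over 5.5 months (MEZZO-based). Both pairs give a hazard ratio (HR) of 0.80.
- Assumed, because the documents give none: residual prevalences, comorbidity effects, and a two-sided 5% test.

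**1. Hazard ratio, case (a)**

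With prevalences p_T and p_C and comorbidity hazard ratio h, the estimate is approximately 0.80 × [1 + p_T(h − 1)] / [1 + p_C(h − 1)]. With h = 1.5:

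- 7.5% versus 5.0%: 0.80 × 1.0375/1.025 = 0.80 × 1.0122 = 0.810
- 15% versus 10%: 0.80 × 1.075/1.05 = 0.819
- 20% versus 10%: 0.80 × 1.10/1.05 = 0.838, or 0.837 when person-time is worked out exactly with constant hazards over 11 months

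The standardised difference is 0.025/√[(0.0694 + 0.0475)/2] = 0.10 in the first setting and 0.10/√[(0.16 + 0.09)/2] = 0.28 in the third.

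These figures assume that the points offsetting the comorbidity in the CCI carry no risk themselves. Suppose instead that the comorbidity scores one point and each other point has HR 1.2. Treating the other points as Poisson, the offset multiplies the result by about exp(0.2 × −0.10) = 0.980 at 20% versus 10%, giving about 0.82.

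**2. Hazard ratio, case (b)**

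Setting: 20% versus 10%, h = 1.5, one point for the comorbidity, and a mean of 0.5 other CCI points in both groups. Constant-hazard models fitted to expected counts gave:

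| Model | Other points HR 1.0 | Other points HR 1.2 |
|---|---|---|
| CCI only | 0.831 | 0.818 |
| Own term plus rest of CCI | 0.800 | 0.800 |

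**3. Hazard ratio bias relative to precision**

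The SE of the log HR is about 1/√(d × 1/3 × 2/3), where d is the number of events.

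- PRIMO: d = 4,200(1 − e^−0.308) + 2,100(1 − e^−0.2464) = 1,113 + 459 = 1,572, so SE = 0.0535.
- MEZZO: d = 268 + 108 = 376, so SE = 0.109.

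A shift from 0.80 to 0.810 is ln(1.0122) = 0.0121, which is 0.23 SE (PRIMO) or 0.11 SE (MEZZO). A shift to 0.837 is ln(0.837/0.800) = 0.0452, which is 0.84 or 0.41 SE.

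**4. Cost**

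Assume a linear comparison, equal mean CCI, 7.5% versus 5.0%, and a comorbidity that adds 0.6 SD of cost beyond its CCI points.

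- Bias = 0.6 × (0.075 − 0.050) = 0.015 SD
- SE = √(1/2,100 + 1/4,200) = 0.0267 SD
- Ratio = 0.015/0.0267 = 0.56 SE
- False positives = Φ(−1.96 + 0.56) + Φ(−1.96 − 0.56) = 0.081 + 0.006, about 9%

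**5. What collinearity would cost**

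The variance of the Tio coefficient depends on how well the covariates predict treatment, not on how they correlate with each other. At 7.5% versus 5.0% (overall 5.83%, SD 0.234), the correlation with treatment is 0.025 × √(2/9)/0.234 = 0.05. The variance inflation is 1/(1 − 0.0025), about 1.003. Giving the comorbidity its own indicator costs almost nothing.

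**The case against.** The strongest reply is that harm needs several things at once. Matching must fail on a listed comorbidity although it is in the propensity score, along with the CCI, under 1:2 nearest-neighbour matching with a caliper. That comorbidity must be a CCI component. The CCI must stay balanced or fit it badly. And the condition must affect the outcome beyond its points. Nothing in the documents shows this combination to be likely. This stands, and it limits the point to residual imbalance. It does not remove the point, because section 9.7.1 itself plans for residual imbalance and the sentence applies in exactly that case.

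A second reply is that the sentence is only an example within a correlation check, perhaps meant to avoid counting one condition twice when both terms would enter. That is a fair reading of the intent. But the wording is categorical, has no correlation threshold, and makes no exception for an unbalanced component. An analyst could follow it literally.

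Stronger inferences are tempting, and the documents do not support them:

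- A reader might infer that all nine listed items are affected. The documents do not list the CCI components, so the number cannot be settled. The sentence only presumes some overlap.
- A reader might infer that the cost results will be materially biased. Section 9.7.1 names a Cox model for the primary outcome and negative binomial regression for the rate, but specifies no model for cost. The linear cost comparison above is an assumption.
- A reader might infer that no covariate should ever be dropped for correlation. The problem does not require so broad a rule.

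**Conclusion.** The point holds as an internal conflict in section 9.7.1. Read literally, the collinearity example overrides the commitment to adjust, leaving a detected imbalance in a CCI component wholly unadjusted (CCI balanced) or partly adjusted (CCI in the model).

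The likely size is modest. At a standardised difference of about 0.10 and a comorbidity hazard ratio of 1.5, the primary hazard ratio moves by about 0.01, under a quarter of a standard error. The illustrative cost bias is about half a standard error. The shift to about 0.84 needs 20% versus 10% prevalence to survive matching, a standardised difference of 0.28. That is large for a variable in the propensity score, though no stated balance threshold excludes it. All prevalences and comorbidity effects here are assumed.

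It would be wrong to conclude that the primary result is shown to be biased, or that the matching strategy fails. The documents support a correctable gap in the adjustment rule, worth closing because closing it costs almost nothing.

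**What to change.** Replace the example sentence in section 9.7.1 with a statement to this effect: any Table 1 comorbidity found unbalanced after matching enters the outcome model as its own indicator, even if it is a component of the CCI; if the CCI also enters, it may be recomputed without that component to avoid double counting.

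The correlation check can otherwise stay. The new sentence will work only as well as the definition of imbalance, so naming a balance measure and threshold in the same paragraph would help.

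The cost is one sentence. The indicators are already Table 1 matching parameters, so no new data are needed, and by the calculation above the loss of precision in the treatment effect is negligible.
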